As allopurinol is classified as FDA class C during pregnancy pregnant women will not be allowed in the study. Women with recent deliveries or third trimester pregnancy losses in the previous 3 months will be excluded because of unpredictable effects on FMD. A special question about the use of azathioprine will be included, since this can have a severe interaction with allopurinol.⁷⁸ Participants with serious medical conditions that in the investigator's judgment pose an unacceptable risk for exposure to a fixed dose of allopurinol (e.g. advanced heart failure, advanced liver disease or cirrhosis) will also be excluded.

H. Data collection and Statistical Analyses (see also Data Analysis plan)

Measures of central tendency (sample mean, sample media) and dispersion (sample variance, sample standard deviation) will be calculated for all outcome variables (e.g., hsCRP, endothelial function, and BP on ABPM) and covariates (e.g. age, race, etc.). For outcome variables, distributional properties will be evaluated using histograms and normal probability plots. When the assumption of normality is questionable, outcome

variable transformations will be examined to determine if the transformed variables approximate a normal distribution. will be transformed to achieve normality. Of the main study measures, we anticipate the distribution of hsCRP to be highly skewed. Consistent with prior studies, we will log transform hsCRP values for analysis. Possible outlying or inconsistent values will be detected and explored

Aim 1a: ULT and change in BP. The change in the average weighted 24-hour mean SBP and DBP will be compared among participants during the active treatment and placebo phases by paired t-test analysis.

Aim 1b: ULT and change in FMD. The change in the FMD will be compared among participants during the active treatment and placebo phases by paired t-test analysis.

Aim 1c: ULT and change in hsCRP. For each participant, we will first calculate the change in log transformed hsCRP from the beginning to the end of each crossover phase. The lack of an effect for the treatment sequence on the relative treatment responses will be confirmed using a treatment by sequence interaction term. Next, the within-participant change in hsCRP will be compared during the allopurinol treatment and placebo phases by paired t-test analysis.

Assessing differential treatment effects by race/ethnicity

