As mentioned above, it is anticipated that the distribution for hsCRP will be skewed, and thus, we will log transform hsCRP. The sample size for the study is based on having 90% statistical power, assuming a two-tailed alpha error of 5% and a within person correlation of log transformed hsCRP between measurements of 10%. The intra-person standard deviation for log transformed hsCRP has been reported to be 0.52 log mg/L on serial measurements extending into a one year period.⁷⁹ To detect a difference in log transformed hsCRP of 0.25 (log mg/L) will require a sample size of 93 participants with complete hsCRP measurements (i.e., from baseline and closeout visits for each of the study phases). This is equivalent to a net reduction of hsCRP of 25% (e.g., from 2 mg/L to 1.5 mg/L or from 1 mg/L to 0.75 mg/L). This difference was chosen as it represents approximately half of one standard deviation in log-transformed hsCRP and is a meaningful decline to be observed over a four week period. Although we expect minimal loss to follow-up, we have taken the conservative step of increasing the sample size to account for 20% of participants not having complete data. Thus, we will recruit and randomize 112 participants for the proposed trial. For comparing differences in the net reduction in hsCRP for African Americans in comparison to other races/ethnicities, with 46 African Americans and 46 other races/ethnicities, we will have 90% statistical power to detect a differential reduction in log transformed hsCRP of 32 log mg/L (e.g., a 10 log mg/L reduction in whites and a 42 log mg/L reduction in African Americans).

Table 4. Statistical Power for Aim 2			
Proportion of Outcome Variance Explained by Control Variables	Incremental increases in R² due to the addition of change in serum urate in the presence of the control variables		
	.05	.075	.10
.10	.64	.82	.92
.20	.69	.87	.95
.30	.75	.91	.97

Power and sample size for aim 2

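### Randomising 112 allows for 17% incomplete data from 93 completers, not the stated 20%; a minor slip, correctable in the text

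*Combined protocol and SAP*

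**What the plan says.** The trial size is set in section 1a.H, Calculation of sample size, in the hsCRP paragraph (headed as aim 1a). For 90% power at two-sided 5% and a difference of 0.25 log mg/L, the plan "will require a sample size of 93 participants with complete hsCRP measurements". The inputs are "a within person correlation of log transformed hsCRP between measurements of 10" per cent, and a standard deviation: "The intra-person standard deviation for log transformed hsCRP has been reported to be 0.52 log mg/L".

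The paragraph then turns to missing data. It opens with "Although we expect minimal loss to follow-up", continues that "we have taken the conservative step of increasing the sample size to account for 20% of participants not having complete data", and concludes: "Thus, we will recruit and randomize 112 participants for the proposed trial".

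Section 5b (Participant Retention) sets a retention target of 80%. Section 7a (Eligibility criteria) continues enrolment until 112 are in, and section L.1 gives 112 as the goal.

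**The concern.** The 20% is described as a share of the participants, so the number randomised should be the required completers divided by 0.8. The printed 112 looks instead like the required completers multiplied by 1.2, which gives a smaller allowance. This paragraph fixes the trial size. A reader would conclude from it that 93 complete participants are secured up to 20% loss. If that is wrong, the trial could meet its own retention target exactly and still miss the number it says it requires.

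**Working it through.** **Inputs.** From the hsCRP sample-size paragraph: 93 completers, 20% incomplete, 112 randomised, two-sided alpha 0.05, power 90%, difference 0.25, SD 0.52, correlation 0.10. From section 5b: 80% retention.

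**Step 1. Reproduce 112.**
- Multiplying: 93 x 1.20 = 111.6, rounded up to 112. This matches the plan.
- Dividing by the completing fraction: 93/(1 - 0.20) = 116.25, rounded up to 117. This does not match.
- Check: 117 x 0.80 = 93.6, at least 93; 116 x 0.80 = 92.8, too few.

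**Step 2. What 112 allows for.**
- Loss that still leaves 93: (112 - 93)/112 = 19/112 = 17.0%.
- Completers at 20% loss: 112 x 0.80 = 89.6, so 89 to 90, which is 3 to 4 below 93.

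**Step 3. Reproduce 93.** The normal approximation is n = (1.960 + 1.282)^2 x SD_d^2 / 0.25^2, where SD_d is the SD of the within-person difference. The exact n uses the paired t-test (noncentral t).
- Two values, correlation 0: SD_d = 0.52 x sqrt(2) = 0.735; approximation 90.9, exact n = 93. This matches.
- Two values, stated correlation 0.10: SD_d = 0.52 x sqrt(2 x 0.9) = 0.698; approximation 81.8, exact n = 84.

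Two further readings serve only to bound the effect of the slip. One takes 0.52 as already the SD of the paired difference. The other takes it as a single-measurement SD and compares two phase changes, since section H (Aim 1c) analyses "the change in log transformed hsCRP from the beginning to the end of each crossover phase". With four values equally correlated at 0.10, that gives SD_d = 0.52 x sqrt(4 x 0.9) = 0.987.

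**Step 4. Power for 0.25 at 93, 90 and 89 completers (paired t).**

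| Reading | SD_d | n for 90% | 93 | 90 | 89 |
|---|---|---|---|---|---|
| Two values, correlation 0 | 0.735 | 93 | 90.0% | 89.1% | 88.7% |
| Two values, correlation 0.10 | 0.698 | 84 | 92.8% | 92.0% | 91.7% |
| 0.52 is the SD of the difference | 0.520 | 48 | 99.6% | 99.5% | 99.4% |
| Four values, correlation 0.10 | 0.987 | 166 | 67.7% | 66.2% | 65.7% |

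Across the rows, going from 93 to 89-90 completers costs between 0.1 and 2.0 points. On the first row, the only one that yields 93, the cost is 0.9 to 1.3 points, and the difference detectable at 90% power moves from 0.250 to 0.254-0.255.

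**The case against.** The best defence of 112 is that the size was raised by 20%, which is what 93 x 1.2 does. The sentence does not say that: its 20% refers to participants without complete data, and the 80% retention target in section 5b points the same way. No section offers another allowance.

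A second defence is that 20% is a cautious margin, because the plan expects little loss. That stands. At any loss up to 17% the 93 are reached and nothing changes.

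A third is that the consequence is negligible. That largely stands too: a power change of about 1 point is small beside the uncertainty in a standard deviation borrowed from another study.

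A reader might go further and infer that the protection of 90% power ends at 17% loss. The documents do not support that as a general statement. It holds only if the variance is the one that reproduces 93, and that variance leaves out the stated 10% correlation. With that correlation and a two-value difference, 84 completers are enough, so 112 keeps 90% power up to 28/112 = 25% loss. On the four-value reading there was no 90% power at 93 to protect, but that reading assumes 0.52 is a single-measurement SD, whereas the plan calls it intra-person and its source cannot be checked here. The slip is therefore no evidence that the trial is underpowered.

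**Conclusion.** The stated allowance is wrong: 112 randomised covers 17.0% incomplete data from 93 completers, and 20% would need 117. That conclusion rests only on three figures in one paragraph and on reading 20% as a share of participants. At 20% loss the trial is 3 to 4 completers below its own stated requirement.

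The effect on power is small and depends on a variance the plan does not fully specify: about 1 point on the variance that gives 93, with power remaining above 90% on the stated correlation for a two-value difference. Severity is minor. A reader might infer that five more participants must be enrolled; the size of the effect does not justify that.

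**What to change.** Keep 112 and change the text in one of two ways.

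1. State that 112 allows for 17% of participants lacking complete data while keeping 93 completers.
2. Keep the 20% margin and state hsCRP power at 89-90 completers. Give the variance and correlation used, because 93 does not follow from the stated 10% correlation. On the variance that does give 93, the figure is 88.7-89.1%.

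The cost is a sentence or two; enrolment and procedures are unchanged.

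The following are separate points and not part of this correction: the variance basis of 93 itself, the SBP and DBP main-effect figures, the FMD and hsCRP race differences, the n behind Table 4, and the 25% wording with its unstated log base.

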- The participant's voluntary agreement to participate in a research study without coercion or undue influence.
- An optional participation in future research by allowing samples to be biobanked.
- Complete disclosure of any appropriate alternative procedures and their risks and benefits
- Disclosure of the extent of confidentiality that will be maintained
- Statement of compensation and/or medical treatment available if injury occurs
- Name, address, and telephone number of the Principal Investigator

If there is a change in any of the study procedures that may affect the participant, the informed consent document will be revised and approved by the IRB. Any participants active within the study prior to a change in procedures will sign the amended consent form. Per NIH policy, the signed consent forms will be kept as part of the study record for at least 7 years after completion of the study. Participants can withdraw their consent at any time by informing the study coordinator. Additionally, all participants will be provided with descriptions of allopurinol hypersensitivity induced rashes and specific instructions to contact the study staff immediately should a rash appear.

The UAB study staff will:

- Provide participants with adequate information concerning the study procedures and scope
- Provide adequate opportunity for the participant to consider all available options
- Respond to the participant's questions and concerns
- Ensure that each participant understands all information provided
- Confirm acceptable birth control is being used
- Obtain the participant's written voluntary consent to participate

- Sign the consent form as the person obtaining consent and functioning as a third-party witnesses
- Provide participants with a copy of the consent form
- Keep the signed form in the participant’s binder
- Attempt to schedule an early end of study assessment in the case of study drug discontinuation

Table 3. Schedule of visits and evaluations

Visit description / Study Procedures	Treatment Phase										
	Screening	Run-in period	Phase 1				Washout period	Phase 2 (crossover)			
	Weeks										
Male participant (original)	0	1-2	3	4	5	6	7-10	11	12	13	14
Male participant (revised)^{††}	0	1-2	3	4	5	6	7-8	9	10	11	12
Female participant (original)	0	1-4	5	6	7	8	9-12	13	14	15	16
Female participant (revised)^{††}	0	1-4	5	6	7	8	9-10	11	12	13	14
	Visit 1		Visit 2			Visit 3		Visit 4			Visit 5 (final)
Informed consent	X										

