the % change is considered positive. Mean and standard deviations were calculated at the beginning and end of allopurinol and placebo phases for FMD.

G. Study Drug

The subjects will be randomized to receive allopurinol as ULT, at a daily dose of 300 mg once daily by mouth. Because of the crossover design of this study, all subjects who complete the protocol will be exposed to the active compound at some point in the study. Allopurinol will be purchased in bulk quantity through the UAB Investigational Drugs Pharmacy, which will also oversee the process of over-encapsulation with cellulose of the active medication and placebos, handle medication storage, distribution, and assignment of randomization sequence. The centralized management of the medication will allow maintenance of a double blind trial. A research nurse will contact participants approximately a week after the initiation of both intervention phases to ask if the participant has any medication concerns and to encourage compliance. Adherence to the medication will be recorded by pill counts at the follow-up study visits and consumption of at least 80% will be required to consider the participant compliant. A non-compliant participant will continue in the study and enter analyses as mandated by the intention-to-treat study design. At the end of the study, biobanked plasma samples (1.0-1.5 mL) will be evaluated for levels of allopurinol and the metabolite, oxypurinol, to determine an objective measure of study drug adherence. An amendment approved by the UAB IRB in September of 2017 allowed for testing oxypurinol and allopurinol prospectively on all participants enrolled (previously restricted to biobanked samples).

Individuals with transaminases or alkaline phosphatase values more than double the upper limit of normal will be excluded. The initial plan was to exclude subjects taking hypertension medications (including diuretics, that some participants do not regard as hypertension treatments), as this will have an unpredictable effect on the study outcomes. An amendment approved in 10/2015 allowed later for inclusion of individuals in stable doses of calcium channel blockers.

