Comparison in the mean change achieved in the allopurinol treatment minus placebo phase between African Americans and other races/ethnicities will be performed initially using a t-test for independent samples. If differences are identified in the distribution of covariates, then the analysis will be completed with analysis of variance.

Assessing change in serum urate on change in hsCRP, FMD, and blood pressure

For this aim, the independent variable is change in serum urate and the outcome is change in hsCRP, FMD, and BP. First, participant factors associated with a significant change in serum urate will be identified using unadjusted age, race/ethnicity, and gender adjusted linear regression models. The correlation between change in serum urate with change in hsCRP, FMD, and SBP and DBP will be calculated using Spearman correlation coefficients. Using linear regression models, the association between changes in serum urate with changes in levels of each outcome, separately, will be determined. Models will include initial adjustment for age, gender, and race/ethnicity with subsequent models adjusted for other potential confounders (e.g. estimated glomerular filtration rate). In analyzing the association of change in serum urate on change in BP, we will additionally adjust for hsCRP and FMD, individually and together. The reduction in the association (i.e. beta coefficient) between change in serum urate and change in BP from before to after adjustment for these variables will provide insight into the degree that these mechanisms mediate the relation between ULT and BP reduction.

With 56 African Americans and 56 other races/ethnicities, we will be able to detect a difference in the increase of FMD of 1.48% for allopurinol versus placebo in African Americans compared to other participants.

The primary analyses will be on an intent-to-treat basis. All statistical analysis will be performed using SAS statistical software (SAS, Cary, NC) by analysts masked to randomization assignment. All study related information will be entered into a study database. This database will be maintained on a secure computer with access limited to study personnel only.

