This study will enroll women between the ages of 18-40 years, at which age we expect a greater majority to be fertile. If pregnancy occurs during the active treatment study period, there is a theoretical risk for the unborn as allopurinol is considered FDA class C during pregnancy. Untreated hypertension during the early pregnancy can also carry a small risk. Pregnant women will not be allowed in the study because allopurinol is classified as FDA class C during pregnancy, additionally prisoners, and institutionalized individuals will be excluded. Proper birth control methods for male and female participants will be confirmed and discussed during the screening visit.

8. Psychosocial risks

There are no obvious psychosocial risks

J. Potential Benefits

Currently, cardiovascular events caused by hypertension are the leading cause of morbidity and mortality in patients with gout and in the general population. If the addition of urate-lowering therapy to the standard therapy for hypertension reduces cardiovascular morbidity through improvement in endothelial function and inflammation in patients with hyperuricemia and those in the higher percentiles of normal serum urate concentration, this knowledge might have a significant impact on the quality of life of a large proportion of the general population.

K. Withdrawal of Participant Consent and Discontinuation of Study Drug

Participants can withdraw their consent at any time by informing the study coordinator.

This may include but is not limited to the following

- a. The subject deciding to withdraw consent for study
- b. An intolerable adverse event as judged by study investigator and/or participant
- c. The subject discontinuing acceptable birth control methods or becoming pregnant
- d. The subject enrolling in a conflicting investigational drug trial
- e. The participant BP > 160/110 between visit 2-5

If the study drug is discontinued, unless the subject withdraws consent, the subject will be followed for the full treatment period and all data will be collected as scheduled. Attempt will be made to schedule an early end of study assessment in the case of study drug discontinuation

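### The intent-to-treat label sits on a complete-pairs analysis for FMD and hsCRP, and the rules for follow-up after stopping study drug are not reconciled

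*Combined protocol and SAP*

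**What the plan says.** Follow-up: Section K states that, unless consent is withdrawn, after study drug is stopped "the subject will be followed for the full treatment period and all data will be collected as scheduled". The next sentence reads "Attempt will be made to schedule an early end of study assessment in the case of study drug discontinuation". The staff duties listed under Informed Consent in Section F carry only the second instruction: "Attempt to schedule an early end of study assessment in the case of study drug discontinuation".

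Section K also lists pregnancy and blood pressure above 160/110 among its withdrawal and discontinuation events, ahead of the continued-follow-up rule. Section I (item 5) and Section 7b exclude a participant whose blood pressure is still elevated when rechecked 24 hours later. Section K, further on, and Section 7b withdraw a participant with a confirmed pregnancy.

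Analysis: Section H says "The primary analyses will be on an intent-to-treat basis". It says that the change in FMD "will be compared among participants during the active treatment and placebo phases by paired t-test analysis", with the same method for 24-hour blood pressure and for log hsCRP. Section G adds "A non-compliant participant will continue in the study and enter analyses as mandated by the intention-to-treat study design". Section F provides multiple imputation for ABPM when a compliant recording cannot be obtained. The text gives no missing-data method for FMD or hsCRP; Section 14d covers form completion only. The hsCRP sample-size paragraph (headed aim 1a) requires 93 participants with complete measurements in both phases and reaches 112 by "increasing the sample size to account for 20% of participants not having complete data".

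**The concern.** An intent-to-treat statement leads a reader to expect that randomised participants are analysed whether or not they finished treatment. A paired t-test needs two within-phase changes per person, so a participant with a complete Phase 1 and no Phase 2 contributes nothing. The same holds for the race comparison, which uses allopurinol minus placebo. Section F lists FMD and hsCRP among the primary outcome markers, and these are the outcomes with no missing-data rule.

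The follow-up wording decides how many people fall into that gap. If one coordinator treats the early assessment as an extra and another treats it as the last visit, similar participants end up with different data.

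Aim 2 is exposed as well. It regresses change in blood pressure on change in urate, then adds hsCRP and FMD and reads the drop in the coefficient as mediation. If the models before and after adjustment rest on different participants, part of any drop may reflect who is in each model.

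**Working it through.** **1. Who enters which analysis, as written**

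| Participant | ABPM | FMD and hsCRP, paired t-test | Mixed model on within-phase change |
|---|---|---|---|
| Stops capsules, measured at Visits 2 to 5 | In, as randomised | In, as randomised | In |
| Attends all visits, one inadequate ABPM recording | Imputed | In | In |
| Complete Phase 1, no Phase 2 | Not clearly covered by the imputation rule | Out | Phase 1 change used |
| Stops in week 2 of Phase 1, seen only at an early visit | No week-4 value | Out | Out, unless the early value is substituted |

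The third row is the analysis gap. The fourth row depends on how Section K is read.

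**2. The plan's own figure**

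Inputs from the hsCRP paragraph: SD 0.52, difference 0.25, two-sided alpha 5%, power 90%. With SD of the paired difference 0.52 × √2 = 0.735, an exact paired t-test needs 93 participants, as stated. (This reproduces only without the stated 10% correlation; with it, the exact figure is 84. That is a separate matter.) The allowance is 93 × 1.2 = 111.6, rounded up to 112.

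**3. Size of the allowance**

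- 112 − 93 = 19 participants, or 19/112 = 17%.
- If instead 20% of 112 are incomplete, 112 × 0.8 = 89.6, so 89 complete pairs remain. Power on the inputs in step 2 is then 88.7%, against 90.0% with 93 and 94.6% with 112.

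**4. What using the single phases could recover**

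Assume 93 complete pairs plus 19 participants with Phase 1 only, split 9.5 per treatment, with correlation ρ between the two within-phase changes and common variance σ².

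- Variance of the treatment difference, pairs only: 2σ²(1 − ρ)/93.
- Variance with the single phases added: 2σ² / [93/(1 − ρ) + 9.5].
- Ratio: 1 + 9.5(1 − ρ)/93. A period term leaves it unchanged under the equal split.

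| ρ | Ratio | Completer equivalents, 9.5(1 − ρ) | Reduction in standard error, 1 − 1/√ratio |
|---|---|---|---|
| 0.1 | 1.092 | 8.6 | 4.3% |
| 0.3 | 1.072 | 6.7 | 3.4% |
| 0.5 | 1.051 | 4.8 | 2.5% |

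Reading the plan's 10% as ρ is an assumption. The sample-size text describes it as a within-person correlation between measurements for hsCRP and as a within-period correlation of change for FMD. The range 0.1 to 0.5 is shown for that reason.

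**The case against.** The strongest reply is that the plan is closer to intent-to-treat than this suggests. Section G keeps non-compliant participants in the study and in the analysis, so a drug-stopper measured in both phases is analysed as randomised. Section F imputes some ABPM data. An attempted early visit can coexist with scheduled ones. A paired t-test is conventional for a crossover, and the plan says openly that it is sized on completers and expects minimal loss to follow-up. Section H also points to a data analysis plan that is not separately present in the text.

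Most of this stands, and it rules out three stronger readings that a reader might infer:

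- That the two Section K sentences are incompatible, or that the early assessment cancels Phase 2. Neither is stated; the text is ambiguous.
- That the paired tests discard every drug-stopper on every outcome. They discard people without two evaluable changes, and for ABPM the imputation rule covers some of these.
- That those lost are mainly people who could not tolerate the capsule. An intolerable adverse event is one listed reason, but no discontinuation rate or breakdown is given, and the 20% allowance is for incomplete data of any cause.

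The reply does not answer the case of one evaluable phase. Section G helps only those who are measured. The imputation rule is worded for recordings that fall short, names no model, and does not clearly reach a phase never entered.

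**Conclusion.** The point holds in limited form. On the text available, the primary analysis is a complete-pairs analysis for FMD and hsCRP under an intent-to-treat label. Blood pressure may rest on a different set of participants. The wording on follow-up after stopping drug is unreconciled across Section F's staff list, Section I, Section K and Section 7b.

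The gain in precision from using single phases is small: at most about 5 to 9 completer equivalents. That is a ceiling. It needs all 19 participants in the allowance to have a usable Phase 1 and a between-phase correlation between 0.5 and 0.1; with fewer usable phases it is less. It cannot be attributed to drug-stoppers, and neither can a selection bias be sized, because the documents give no discontinuation rate. The case for change rests on matching the analysis to its label at little cost, not on a demonstrated bias.

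**What to change.** 1. **Analysis.** For ABPM, FMD and log hsCRP alike, make the primary analysis a linear mixed model on within-phase change, with fixed effects for treatment and period and a random participant effect. Include every randomised participant with at least one evaluable phase. Keep the paired t-test as supportive. Describe the analysis set in those terms, since anyone with no evaluable phase is still left out. The cost is a few lines of SAS and some protocol wording. The downside is that the model assumes data are missing at random, which should be stated.

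2. **Follow-up wording.** The sponsor should reconcile the Section F staff list, Section I item 5, Section K and Section 7b. The text should say whether the early assessment is additional to the scheduled visits or replaces them, whether the full treatment period means one phase or both, and how continued follow-up relates to the exclusion for blood pressure and the withdrawal for pregnancy. No clinical rule is proposed here. For the analysis, state that an early off-schedule assessment is not used as the week-4 value.
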